10.1.3 Adverse Drug Reaction (ADR)

An Adverse Drug Reaction (ADR) is any untoward and unintended response to an IMP that is considered to have a reasonable possibility of a causal relationship with the treatment, i.e., the relationship cannot be ruled out.

10.1.4 Serious Adverse Event/ Serious Adverse Drug Reaction (SAE/ SADR)

A Serious Adverse Event (SAE) or Serious Adverse Reaction (SADR) is any untoward medical occurrence or effect that at any dose:

- Results in death
- Is life-threatening (note: the term “life-threatening” refers to an event in which the patient was at risk of death at the time of the event; it does not refer to an event which hypothetically may cause death if it is more severe)
- Requires inpatient hospitalization (overnight stay) or prolongation of existing hospitalization
- Results in persistent or significant disability or incapacity
- Is a congenital anomaly or birth defect
- Is of special interest at the Investigator’s discretion
- Or other medically important condition.

Other medically important conditions are defined as important medical events that may not be immediately life-threatening or result in death or hospitalization but may jeopardize the patient or may require intervention to prevent one or more of the outcomes listed in the definition above.

Examples of such events are intensive treatment in an emergency room or at home for allergic bronchospasm, blood dyscrasias or convulsion that does not result in hospitalization, or development of drug dependency or drug abuse.

However, medical judgement has to be exercised in deciding whether an event is serious in any other situations considered medically relevant.

The evaluation of the AE as being serious or not-serious is made independently of any attribution of causality. Events requiring treatment on an emergency outpatient basis (not resulting in admission to hospital) and not fulfilling any of the definitions of seriousness given above are NOT considered to be SAEs.

10.1.5 Medical Events not to be Considered AEs or SAEs

The following events should not be recorded as an AE/ SAE if recorded at the screening period and/or the basic examination of a clinical trial:

- A pre-planned procedure, e.g., surgery and invasive procedures, unless the condition for which the procedure was planned has worsened since Baseline 1.
- Complications to pre-planned procedures should be recorded as AEs.
- A pre-existing condition found as a result of screening procedures.
- Pregnancy is not considered to be an AE.

Note: Any worsening in severity or frequency of a concomitant illness or any new illness diagnosed in the trial period has to be regarded as AEs/ SAEs.

10.1.6 Unexpected Adverse Reaction (UAR)

An Unexpected Adverse Reaction (UAR) is an ADR, the nature or severity of which is not consistent with the information available on the IMP reference safety information.

10.1.7 Suspected Unexpected Serious Adverse Reaction (SUSAR)

A Suspected Unexpected Serious Adverse Reaction (SUSAR) is a serious ADR, the nature or severity of which is not consistent with the applicable reference safety information.

10.2 Criteria for Clinically Relevant Abnormal Findings

The assessment whether abnormal laboratory findings are of clinical relevance will be done by the Investigator and documented in the electronic Case Report Form (eCRF).

10.3 Recording of AEs

All AEs that occur during the entire course of the trial after the patient has signed the informed consent are to be collected and reported in the eCRF, regardless of whether they are reported by the patient, elicited by Investigator questioning, detected through physical examination, or by other means.

For the case that AEs are still ongoing at the end of the trial, Investigators should make a reasonable effort to obtain a final status of the AE and, where possible, an end date even if the end date is later than the final trial-specific visit for the patient concerned. Information dated after the end of the trial for the patient concerned will not be part of the data collection in the eCRF.

10.4 Evaluation of AEs

As far as possible, each AE is described by:

- Duration (start and end dates)
- Start/ end of (investigational) medication

- Intensity (mild, moderate, severe)
- Investigator assessed causality (relationship to the IMP)
- Action(s) taken (change of investigational medication, treatment of AE etc.) including start and end of respective action
- Concomitant diseases and respective medication in general
- Outcome.

10.4.1 AE Intensity

AE intensity determined by the Investigator on the basis of his/her direct observations or the patient's reporting:

- Mild: causes no limitation of usual activities; the patient may experience slight discomfort
- Moderate: causes some limitation of usual activities; the patient may experience annoying discomfort
- Severe: causes inability to carry out usual activities; the patient may experience intolerable discomfort or pain.

10.4.2 AE Causality

Any AE has to be judged for causality (relationship to investigational medication and relationship to trial procedures). The Investigator will assess causal relationship between the IMP and all AEs whether there is a reasonable possibility that the drug caused the event.

The assessment will be based on the question 'Do you consider that there is a reasonable possibility that the AE may have been caused by the IMP?'. The evaluated answer will be 'yes' or 'no'.

In case a reasonable possibility cannot be excluded, reasonable possibility of causal relationship should be considered until further evidence will be available to exclude it.

For AEs the causal relationship to other medications and trial procedures will also be assessed. In case of reasonable possibility that the AE may have been caused by trial procedures or other medication the evaluated answer will be 'yes'.

Data collection will be set up in a way that allows to distinguish between IMP relatedness and procedure relatedness.

Emerging information from procedure-related AEs, if any, will be taken into account for continuous risk-management and re-assessment if the intended procedures remain adequate. Procedures will be revised where there is evidence that risk or burden for the trial participants is not acceptable.

10.4.3 Handling of AEs

If an AE occurs, appropriate diagnostic and therapeutic measures are to be taken and the IMP has to be discontinued if appropriate. Follow-up evaluations of the patient are to be performed until the patient recovers or until the Investigator considers the situation to be no longer clinically significant or until the degree of a permanent disability can be assessed.

Investigators monitor and register all AEs on the AE form of the eCRF at each visit.

For any AE a specific diagnosis rather than signs or symptoms have to be given in the eCRF. In absence of a specific diagnosis, an individual AE form has to be filled in for each sign or symptom to allow proper coding according to Medical Dictionary for Regulatory Activities (MedDRA).

MedDRA coding will be based on the latest version available at trial start throughout the trial to achieve consistency.

Persistent AEs will be entered once in the eCRF until they are resolved or if a new event has to be documented due to deterioration. These AEs will be carefully monitored; further details of monitoring of persistent AEs will be provided in the Monitoring Plan. If an AE is still not resolved at the end of the trial for the individual patient, this will be documented as ongoing at trial completion.

For recurrent AEs, i.e., AEs of the same nature, but with a different date of onset, an individual AE form has to be completed for each of them.

AEs occurring after the termination of the trial individually and/or of the trial in total are to be reported to Biologische Heilmittel Heel GmbH even after the clinical trial has been completed if, in the judgement of the Investigator, there is an association between the event and the previous use of the product under investigation.

10.5 Reporting of Serious Adverse Events (SAEs)

10.5.1 Responsibility of Investigator

If the AE is classified as serious, the Investigator has to complete and also sign the SAE module in the eCRF. It is the responsibility of the Investigator to send the SAE report out of the eCRF within 24 hours after becoming aware of it and print the report out of the eCRF and file it in the Investigator Site File. At the earliest possible date, the SAE report form has to be followed by a detailed report and any documentation that might have become available, e.g., hospital records, autopsy reports, and/or other pertinent documents.

All the above documents will be sent by fax or scan via email to the Drug Safety Department of the designated CRO within 24 hours (see contact details below) and the original of the form will be retained in the patient file (keeping a photocopy in the Investigator Site File). Personal data of the patient have to be deleted or redacted, the patient number and trial code have to be used for patient identification.

For reporting SAEs in the event of technical failure of eCRF, a paper form of the SAE report has to be completed and faxed or emailed as scan within 24 hours using the following contact:

AMS Advanced Medical Services GmbH Safety Department

[contact]

Email: [contact]

At the earliest possible date, the SAE report form has to be completed in the eCRF and procedures described in the first paragraph of this section should be followed. A detailed follow-up report and any documentation that may be available, e.g., hospital case records, autopsy reports, and/or other pertinent documents will be sent via fax or scan via email.

The primary person responsible for Safety at the Pharmacovigilance Department of Biologische Heilmittel Heel GmbH is:

Biologische Heilmittel Heel GmbH
[name]
[name], Germany
Phone: [REDACTED]
[contact]
Email: [contact]

The Qualified Person for Pharmacovigilance (QPPV) at Biologische Heilmittel Heel GmbH is:

[REDACTED]
Biologische Heilmittel Heel GmbH
[name]
[name], Germany
Phone: [REDACTED]
[contact]

Availability in emergency patient safety situation (24 hours/day and 7 days/week)
[contact]

10.5.2 Responsibility of Sponsor

The Sponsor will assess if an SAE is in line with the IMP's existing reference safety information (thus 'expected') or if the SAE is not in line with the existing reference safety information (thus 'unexpected').

All Suspected Unexpected Serious Adverse Reactions (SUSARs) will be reported to the Competent Authority(ies) concerned and to the Ethics Committee(s) concerned as soon as possible but within a maximum of **15 days** (fatal or life-threatening SUSARs within a maximum of **7 days**) of first knowledge by the Sponsor.

Relevant follow-up information of fatal or life-threatening SUSARs will be communicated subsequently within an additional 8 days.

Any circumstances which require a review of the risk-benefit assessment of the IMP will be reported to the Competent Authority(ies) and to the Ethics Committee(s) as soon as possible but within a maximum of 15 days.

Throughout the clinical trial, the Sponsor shall provide the Competent Authority(ies) and the Ethics Committee(s) with yearly safety assessment reports, Development Safety Update Reports (DSURs), which list Suspected Serious Adverse Reactions (expected and unexpected).

The Sponsor shall within 15 days notify the Competent Authority(ies) concerned and the Ethics Committee(s) concerned when the clinical trial has been suspended or interrupted by the Sponsor, giving the reasons for the suspension or interruption.

10.6 Follow-up of AEs

Regardless of the duration of the trial, every patient suffering from an AE must be monitored by the Investigator and/or the Sponsor independently from trial termination at least for SAEs until its complete resolution or until its cause has been established.

10.7 Pregnancy

Females who are pregnant or breastfeeding are not allowed to participate in this clinical trial. Urine pregnancy test will be performed for women of childbearing potential at Screening Visit before first IMP administration to exclude pregnancy. Women are considered of childbearing potential, i.e., fertile, following menarche and until becoming postmenopausal unless permanently sterile. Permanent sterilization methods include hysterectomy, bilateral salpingectomy and bilateral oophorectomy.

A postmenopausal state is defined as no menses for 12 months without an alternative medical cause. A high follicle stimulating hormone (FSH) level in the postmenopausal range may be used to confirm a postmenopausal state in women not using hormonal contraception or hormonal replacement therapy. However, in the absence of 12 months of amenorrhea, a single FSH measurement is insufficient.

Women of childbearing potential must agree to maintain highly effective or acceptable birth control throughout the trial (CTFG 2020).

Highly effective (failure rate of less than 1% per year)

- **Combined** (estrogen and progestogen containing) hormonal contraception associated with inhibition of ovulation: oral, intravaginal, transdermal
- **Progestogen-only** hormonal contraception associated with inhibition of ovulation: oral, injectable, implantable
- **Intrauterine** device
- **Intrauterine** hormone-releasing system
- **Bilateral tubal** occlusion
- **Vasectomized** partner (provided partner is sole sexual partner and if vasectomized partner has received medical assessment of the surgical success)
- **Sexual abstinence** (only if defined as refraining from heterosexual intercourse during the entire period of risk associated with the study treatments)

Acceptable birth control methods which may not be considered as highly effective (failure rate of more than 1% per year)

- **Progestogen-only** oral hormonal contraception, where inhibition of ovulation is not the primary mode of action
- Male or female **condom** with or without spermicide
- **Cap, diaphragm or sponge** with spermicide
- **Combination** of male condom with either cap, diaphragm or sponge with spermicide (**double barrier** methods)

All pregnancies observed during the course of the trial and their outcomes should be reported to the CRO and/or the Sponsor. If a patient becomes pregnant the investigational product should be discontinued immediately and the patient should be withdrawn from the trial. The Investigator or other site personnel will have to inform the CRO and/or the Sponsor within 24 hours of when he or she becomes aware of the pregnancy.

A Pregnancy Report Form should be used for reporting and sending via fax or scan via email to:

AMS Advanced Medical Services GmbH Safety Department

[contact]

Email: [contact]

Contact details of Drug Safety at Heel see in section 10.5.1 above.

The designated CRO and/or Sponsor representative liaise with the Investigator to ensure that all relevant information is provided within 24 hours in case of SAEs and within 30 days for pregnancies without any complications.

Pregnancy itself is not considered as AE, but any complications e.g., congenital abnormalities, birth defects, and spontaneous miscarriages should be handled and reported as SAEs.

11. Statistical Methods and Data Analysis

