5.3 Trial Duration

The First Patient First Visit (FPFV) was in June 2023. A total of 80 patients will be randomized within approximately 32 months. The Last Patient Last Visit (LPLV) is planned to be in January 2026.

The total trial duration for each patient is 37 to maximum 60 days (Table 3). Patients start with a Screening Visit 8 to 28 days prior to first investigational treatment (on Day 0), followed by two baseline visits for a PSG adaptation ('screening') night at Baseline 1/ Day -2 to -1 and the primary outcome relevant PSG night at Day -1 to Day 0, respectively. Patients are randomized to their investigational treatment after completion of visit Baseline 2 / Day 0. Patients will take their investigational treatment for 14 consecutive days (starting at Day 0 to Day 13). Patients will visit the investigational site at Day 12 +2 for a PSG adaptation night and at Day 13 +2 for the primary outcome relevant PSG night. On Day 28 +3 a Follow-up Visit will take place to collect paper-based patient-reported outcome data of BAI, PSQI, PSS-10, SF-36v2 and SSQ-25 questionnaires and the End of Trial (EoT) documentation is to be completed.

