16. Any relationship of dependence with the Sponsor or with the Investigator
17. Active infection/ disease (C-Reactive Protein [CRP] >5 mg/l)
18. Hypertension defined as systolic blood pressure ≥ 140 mmHg (Burnier, 2018)
19. History of neurological, rheumatic, chronic pain, immune, cardiovascular, pulmonary, liver/ kidney, or metabolic disorder within the last 6 months prior to Screening Visit

20. Nocturia
21. Pregnancy (as proven by positive urine pregnancy test at Screening Visit) or breastfeeding
22. Patients with moderate to severe skin allergies and/or eczema
23. Raynaud's disease
24. Donation of blood or platelets 3 months prior to or in-between in-hospital visits.

Patient screening will include blood tests for complete blood count (CBC) and differentials, as well as thyroid hormone and blood glucose; urinary toxicology screens will also be conducted (exclusion criterion number 9). The eligibility of patients based on safety laboratory parameters (except CRP) are at the discretion of the investigator.

The medical history and physical examination will be conducted by a trial physician.

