At **Baseline 1** (Day -2 to Day -1) patients will have their first night at the trial site for PSG adaptation and screening for exclusion criterion 3. Patients complete their electronic sleep diary (adapted from DGSM, on **AMS-ePRO®**) to be kept until the End of Trial (Follow-up Visit/ Day 28+3) and questionnaires on sleep, mood, stress and quality of life. In the evening before the Baseline 1 night urine and breath alcohol tests will be conducted on drugs and alcohol, respectively. After awakening (Day -1) resting state stress parameters in saliva are to be collected (at 5 time points) and every 3 hours (at 4 time points). In the course of the morning, patients will perform neuropsychological tests from the TAP battery. An rsEEG and measurement of resting heart rate and HRV will be performed at approximately 15 minutes prior CPT. Around 12:00 at Day -1 a CPT will be conducted, before and afterwards blood samples will be collected. Patients will complete a subjective pain and stress rating during CPT test.

The following procedures will be performed:

- Urine collection for test on drugs in the evening at Day -2 (section 9.1.11)
- Breath alcohol test in the evening at Day -2 (section 9.1.11)
- Completion of the following questionnaires:
 - a) on paper: BAI, BDI-II, WEIMuS, PSQI, PSS-10, SF-36v2, SSQ-25
 - b) on **AMS-ePRO®**: ESS, ISI, PASA (section 9.1.14)
- PSG for screening of exclusion criterion 3 and for adaptation to the unfamiliar sleep lab environment in the night between Day -2 and Day -1 (section 9.1.1)
- Check exclusion criterion 3 at Day -1
- Collection of 0.5 to 1 ml saliva to measure cortisol, DHEA-S and alpha-amylase at awakening (0 minutes), and after 15 minutes, 30 minutes, 45 minutes, 60 minutes, 3 hours, 6 hours, 9 hours and 12 hours after awakening at Day -1 (section 9.1.2)
- Neuropsychological tests (TAP) at Day -1 (section 9.1.10)
- Resting state EEG, resting state HR and HRV to measure daytime performance at Day -1 (section 9.1.3)
- CPT around 12:00 including subjective pain rating and pain tolerance, heart rate and associated HRV measures, electrodermal activity, and EEG at Day -1 (section 9.1.7)
- Collection of approximately 12.5 ml blood for measuring cortisol, DHEA-S, adrenaline, noradrenaline, inflammation markers (IL-6 and TNF- α) prior to CPT, 20 minutes and 50 minutes after CPT at Day -1 (section 9.1.8)
- Adverse events at Day -2 (section 10)
- Changes in concomitant medication at Day -2

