- Complete sleep diary and stress assessment (in **AMS-ePRO®**).

At **Baseline 2** (Day -1 to Day 0) patients will stay at the site for a second night for PSG. After awakening (Day 0) resting state stress parameters in saliva are to be collected (at 5 time points). Patients will be randomly assigned to treatment group Neurexan® or Placebo with a 1:1 allocation and stratification by sex.

The following procedures will be performed:

- Urine collection for test on drugs in the evening at Day -1 (section 9.1.11)
- Breath alcohol test in the evening at Day -1 (section 9.1.11)
- Baseline 2 PSG night to measure primary, i.e., SE and secondary endpoints, i.e., SOL, WASO, TST, NWAK, and ARI during sleep in the night between Day -1 and Day 0 (section 9.1.1)
- Collection of 0.5 to 1 ml saliva to measure cortisol, DHEA-S and alpha-amylase at awakening (0 minutes), and at 15 minutes, 30 minutes, 45 minutes, 60 minutes after awakening at Day 0 (section 9.1.2)
- Adverse events at Day -1 and Day 0 (section 9.2.1)
- Changes in concomitant medication at Day -1 and Day 0
- Randomization to treatment group at Day 0 (section 11.2)
- Distribution of IMP and instruction regarding use of IMP at Day 0
- Starting IMP treatment after having performed all Baseline 2 assessments at midday Day 0 (section 7.1)
- Complete sleep diary and stress assessment (in **AMS**-ePRO®).

Patients will continue to take their trial treatment for 14 consecutive days (Day 0 - Day 13).

At **Visit 1** (Day 12 to Day 13; +2 days) patients return to the trial site for another PSG adaptation night. A urine and breath alcohol test will be conducted on drugs and alcohol, respectively. After awakening (Day 13) resting state stress parameters in saliva are to be collected (at 5 time points) and every 3-hours (at 4 time points). In the course of the morning, patients will perform neuropsychological tests from the TAP battery. An rsEEG and measurement of resting heart rate and HRV and EDA will be performed at approximately 15 minutes prior CPT. Around 12:00 at Day 13 a CPT will be performed, blood samples will be collected (before CPT and 20 minutes and 50 minutes after CPT) and patients will complete a subjective pain and stress rating. During CPT an EEG will be performed and heart rate and HRV will be measured. Additionally, patients will complete questionnaires on sleep, stress and quality of life on paper (BDI-II, WEIMuS) and on **AMS**-ePRO® (ESS, ISI, PASA).

The following procedures will be performed:

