9.1.11 Urine Test and Alcohol Breath Test

Urine drug screening test and an alcohol breath test will be performed at Screening Visit (Day -28 to -8) and prior to the PSG nights (Baseline 1, Baseline 2, Visit 1 and Visit 2).

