9.1.12 Pregnancy Test

Urine pregnancy test will be performed at Screening Visit/ Day -28 to -8 in women with childbearing potential.

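### The only pregnancy test is 8 to 28 days old at first dose; a repeat on urine already collected at Baseline would be a cheap, minor improvement

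*Protocol*

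**What the plan says.** Section 10.7 does not allow pregnant or breastfeeding women to take part, and states when and why the test is done: "Urine pregnancy test will be performed for women of childbearing potential at Screening Visit before first IMP administration to exclude pregnancy". Section 9.1.12 gives the window: "Urine pregnancy test will be performed at Screening Visit/ Day -28 to -8 in women with childbearing potential". Exclusion criterion 21 defines the condition by that one result: "Pregnancy (as proven by positive urine pregnancy test at Screening Visit) or breastfeeding". The Screening list in section 8.1 and both schedule tables (section 2.2 and Table 3) agree. The procedure lists for Baseline 1, Baseline 2, Visit 1, Visit 2 and Follow-up contain no pregnancy test.

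Section 5.3 gives the interval to treatment: "Patients start with a Screening Visit 8 to 28 days prior to first investigational treatment (on Day 0". Section 8.1 fixes the first dose: "Starting IMP treatment after having performed all Baseline 2 assessments at midday Day 0 (section 7.1".

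Urine is collected again before dosing, for drug testing only. Section 8.1 has "Urine collection for test on drugs in the evening at Day -2 (section 9.1.11" at Baseline 1 and "Urine collection for test on drugs in the evening at Day -1 (section 9.1.11" at Baseline 2. Section 9.1.11 describes the drug and alcohol tests as done at Screening "and prior to the PSG nights (Baseline 1, Baseline 2, Visit 1 and Visit 2".

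Inclusion criterion 8 and section 10.7 require birth control for the whole trial. They accept highly effective methods and also methods with a failure rate above 1% per year. If a pregnancy becomes known, section 10.7 requires treatment to stop, the patient to be withdrawn and the pregnancy to be reported; section 6.3 lists pregnancy as a reason for discontinuation.

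**The concern.** The test has a stated purpose, to rule out pregnancy ahead of the first dose, but its date limits how well it can serve that purpose. A negative result on Day -28 to -8 says nothing about a conception in the following days, and it can miss one too recent to detect at Screening. Nothing scheduled between that result and the first dose would reveal either.

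At stake is whether a woman whom section 10.7 excludes could be randomised and dosed without a check close to treatment. There is a small secondary effect. A pregnancy found before randomisation is a screening failure. One found afterwards forces a withdrawal, and section 6.3 does not replace drop-outs. Type I error, power and the primary analysis are not affected.

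**Working it through.** **The plan's own interval.** First dose is on Day 0 and Screening on Day -28 to -8.
- Age of the test at first dose: 0 - (-8) = 8 days to 0 - (-28) = 28 days, which reproduces the 8 to 28 days in section 5.3.
- Counting both end days gives 9 to 29, which matches the run-in length in the schedule.
- With a repeat on the Day -2 evening sample the result would be 2 days old; on the Day -1 evening sample, 1 day old.

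**Chance per woman.** The protocol gives only the 1% per year boundary, so the higher failure rates are assumptions. With annual failure rate f and d days between test and first dose, the chance of a conception is 1 - (1 - f)^(d/365.25).

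| f per year | d = 8 | d = 28 |
|---|---|---|
| 1% | 0.02% | 0.08% |
| 5% | 0.11% | 0.39% |
| 10% | 0.23% | 0.80% |
| 20% | 0.49% | 1.70% |

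**Expected number over the trial.** The protocol does not give the number of women of childbearing potential. I assume 20, 40 or 60 of the 80 planned patients, with failure rates of 1%, 5% and 10% per year. The days from Screening to Day -2 are 6, 16 (midpoint) and 26. Expected conceptions = women x rate x days/365.
- Low: 20 x 0.01 x 6/365 = 0.003
- Middle: 40 x 0.05 x 16/365 = 0.09
- High: 60 x 0.10 x 26/365 = 0.43

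**Patients who could still benefit.** The revision history for Version 4.0 (27 February 2025) reports 46 patients randomised, so at most 80 - 46 = 34 remain. With the same share of women, that is 20 x 34/80 = 8.5, 40 x 34/80 = 17 and 60 x 34/80 = 25.5.
- Low: 8.5 x 0.01 x 6/365 = 0.001
- Middle: 17 x 0.05 x 16/365 = 0.04
- High: 25.5 x 0.10 x 26/365 = 0.18

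With 1:1 allocation about half would be on Neurexan: 0.0007, 0.02 and 0.09. With the Day -1 sample instead (7, 17 and 27 days), the totals for both arms are 0.002, 0.04 and 0.19.

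These counts are rough in both directions. They include conceptions too recent for the repeat to detect. They leave out pregnancies begun just before Screening, which a repeat could catch.

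**The case against.** The strongest reply is that the document does what it says. The test is done at Screening, which is before first dosing, and every section places it there. A reader might infer a contradiction between section 10.7 and the schedule, but there is none. The point is only that the timing serves the stated purpose imperfectly.

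The test is also not the only protection. Contraception is mandatory from Screening onwards, and women are seen at the site on Day -2, Day -1 and Day 0, so a pregnancy they know of can be acted on before dosing. This stands and lowers the likelihood. It does not close the gap: some accepted methods fail in more than 1% of users per year, contraception started at Screening cannot undo a conception just before it, and the withdrawal rule works only once a pregnancy is known.

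The documented hazard is low. The product is sold over the counter, the trial dose of 6 tablets a day is below the 12 allowed in acute disorders, and section 3.3 states no concerns or apparent risks in pregnancy. That stands too, although the same section calls the data scarce and has none specific to the product. The sponsor nevertheless chose to exclude pregnant women.

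Two further inferences are not supported. A reader might take the Baseline 1 check of exclusion criterion 3 as a precedent for rechecking eligibility. The schedule omits that criterion from the Screening check, and it is first assessed at Baseline 1 because it needs the first polysomnography night. It shows only that an eligibility step before randomisation exists there. Nor does the repeated drug screen imply that a pregnancy test should be repeated: recent drug or alcohol intake can affect that night's recording, which is a different reason.

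**Conclusion.** The gap is real but minor. The only pregnancy test is 8 to 28 days old at first dose, no repeat is scheduled, and a pregnancy beginning or becoming detectable in the run-in would go unnoticed by every scheduled procedure. The dates come straight from the protocol.

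The size rests on assumptions about the number of women (20 to 60 of 80) and failure rates (1% to 10% per year). Across that range the expected number of run-in conceptions is below one for the whole trial and at most about 0.18 to 0.19 among patients who could still benefit, a group that shrinks as recruitment continues. A reader might infer a meaningful fetal risk or a threat to the trial's conclusions. The documents support neither. This is an optional improvement in participant safety and eligibility.

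**What to change.** For patients still to be randomised, repeat the urine pregnancy test in women of childbearing potential on urine already collected for the drug screen, with the result known before randomisation on Day 0. The Day -2 evening sample gives a result in time for the exclusion criterion 3 check on Day -1; the Day -1 evening sample is closest to dosing. Either will do. Extend exclusion criterion 21 to a positive test at Screening or Baseline, and align the synopsis, sections 6.2, 8.1, 9.1.12 and 10.7, and both schedule tables.

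The cost is one strip per woman tested: about 9 to 26 for the remaining patients under the assumptions above, and slightly more if the Day -2 sample is used, since some of those women may then fail exclusion criterion 3. No visit or sample is added. It needs a short amendment through the normal approval process, a small change to the validated eCRF (section 13.3.3 lists pregnancy test results as direct entries) and the check of the consent form that section 12.5 requires. A very recent conception would still be missed, and nothing is added during treatment. The change is best bundled with the next amendment; if none is planned, leaving the schedule as it is would be reasonable.
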